1. PURPOSE OF THE STUDY

a. To address the need for increased support for initiating CGM, we developed a 4-session CGM-focused behavioral intervention called ONBOARD (Overcoming Barriers & Obstacles to Adopting Diabetes Devices). The current mixed methods study had two main goals: 1) to examine the feasibility and acceptability of a pilot of ONBOARD for adults with T1D; and 2) to examine preliminary evidence of the impact of ONBOARD on glycemic outcomes (i.e. time in glucose target range; diabetes distress). We hypothesized that ONBOARD would be feasible and acceptable for adults with T1D and lead to increases in time in range and decreases in diabetes distress.

2. STUDY PROCEDURES

a. Procedures

Once eligibility is confirmed, participants will be consented and enrolled. Once enrolled, a baseline assessment survey will be completed online via a secure site (REDCap) to obtain demographic and psychosocial data. Blood glucose meter and continuous glucose monitor will be downloaded. For participants not currently using CGM but would like to, we will work with the clinical team to get them started via standard clinical procedures. In addition, during our work with them (after the clinical start of CGM), we will use FDA-approved Dexcom guides as reminders of standard resources they have access to for CGM. Next, all participants will schedule four individual, 60-minute visits with study interventionist to complete ONBOARD sessions, each 3 weeks apart. If available, we will ask participants to provide a hemoglobin A1c result obtained in the 3 months prior to study enrollment or obtain this via their medical record. Visits will be conducted via a secure, HIPAA-compliant, videoconferencing software. Sessions will be recorded to ensure consistency and quality of the intervention across participants. Upon completion of 4 intervention sessions, participants will complete a follow-up 30-minute REDCap survey and will participate in a focus group to provide feedback on the intervention.

Blood glucose meter and continuous glucose monitor will be downloaded. If a hemoglobin A1c result was obtained during the course of the study, we will ask participants to provide this or obtain it via their medical record. Focus groups will be audio-recorded and use a semi-structured interview guide to ensure consistency across groups and will aim to elicit feedback about ONBOARD's clarity, health literacy level and comprehension. We will also elicit 1) session-specific feedback; 2) changes in device-specific knowledge and problem-solving skills after the intervention; 3) overall feedback on the intervention.

b. Procedure Risks

The study will be explained as part of the consent process. We will provide detailed information about the study, its purpose, and procedure. Participants will be given enough time to consider carefully their own participation and ask questions about the study prior to providing consent.

c. Use of Deception in the Study

NA

d. Use of Audio and Video Recordings

Intervention sessions and focus groups will be video and audio recorded by the software on Zoom, which is approved for high risk data. Transcripts will be anonymized prior to analysis. No personal identifying information will be included in any transcripts.

e. Alternative Procedures or Courses of Treatment

NA

f. Will it be possible to continue the more (most) appropriate therapy for the participant(s) after the conclusion of the study?

NA

g. Study Endpoint(s)

Analyses are intended to iteratively refine ONBOARD intervention materials. Therefore, quantitative analyses will be descriptive and examine differences between baseline and post-intervention in terms of psychosocial variables, technology attitudes, and health outcomes. Qualitative analyses will use data from focus groups carried out post-intervention. Interviews will be digitally recorded, transcribed and anonymized, reviewed for completeness and accuracy, and then imported into the qualitative software package, NVIVO 10 (QSR International Pty Ltd., 2014). We will use content analysis to code transcripts, resolve discrepancies between coders, and capture key themes for areas of feedback on the intervention to refine each session.

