j. Participation in Multiple Protocols

We will verbally elicit this information from participants. If participants are enrolled in another protocol, we will discuss the study with the PI to determine if it is safe for the subject to enroll in both protocols simultaneously.

k. Payments to Participants

Participants will receive up to an \$100 Amazon gift card upon completion of the study (\$25 for baseline assessment; \$50 for all 4 intervention sessions; \$25 for completing a focus group and survey at the end of the study).

l. Costs to Participants

NA

m. Planned Duration of the Study

The probable duration of the entire study is 2 years. We anticipate screening will require 5 minutes, activate participation in the study will require approximately 3 months, and analysis of participant data will require approximately 1 year. Surveys will require approximately 30 minutes each to complete and ONBOARD sessions and the focus group will require approximately 1 hour each.

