5. RISKS

i. Psychological well-being

Data downloaded from the CGM and the home glucose meter will be collected for the study as measures of diabetes self-management behaviors. Some people may be uncomfortable with researchers' having such detailed information about their daily diabetes habits. Psychological and human factors testing may make study participants uncomfortable. Subjects are free to withdraw from the study at any time. We have psychologists and health care professionals who will be available to help study participants with their stress or anxieties.

ii. Economic well-being

Time away from school and/or work is a potential risk.

iii. Social well-being

Loss of confidentiality is a potential risk.

iv. Overall evaluation of risk

Low

b. Procedures to Minimize Risk

Subjects will continue to receive type 1 diabetes care from their usual provider. Subjects are free to withdraw from the study at any time. For security and confidentiality purposes, subjects will be assigned an alphanumeric identifier that will be used instead of their name.

c. Study Conclusion

Individual subjects will be removed from the study if circumstances develop during the study that, in the judgment of the investigator, make it inadvisable for the subject to continue with the study.

NA

d. Risks to Special Populations

NA

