## STATISTICAL ANALYSIS PLAN

For this pilot study we aimed to recruit between 20 and 40 adults with type 1 diabetes. Descriptive statistics were used to calculate frequencies and means for demographic and medical information. To examine changes from baseline to post-intervention in primary and secondary outcome variables, we used paired t-tests for normally distributed variables and Wilcoxon signed-rank tests for non-normally distributed variables. We then calculated effect sizes (Cohen's d; r). To assess feasibility and acceptability, we calculated percentage of eligible individuals who agreed to participate in the study, and percentage of participants who withdrew or were lost to follow-up. Focus group data was analyzed using content analysis.

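### The follow-up survey and focus group are described only for people who complete all four sessions, so distress change and refinement feedback may come from finishers alone

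*Protocol*

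**What the plan says.** Protocol section 2.a (Procedures) places the end-of-study assessment after the sessions: "Upon completion of 4 intervention sessions, participants will complete a follow-up 30-minute REDCap survey and will participate in a focus group". The four sessions are three weeks apart. The later download of meter and CGM is in a separate paragraph, with no reference to the number of sessions completed.

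Protocol section 2.g (Study Endpoint(s)) says what the data are for: "Analyses are intended to iteratively refine ONBOARD intervention materials". It also names the source of the qualitative material: "Qualitative analyses will use data from focus groups carried out post-intervention".

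Protocol section 4.k (Payments to Participants) splits a maximum of 100 dollars into 25 for baseline, 50 for all four sessions, and 25 "for completing a focus group and survey at the end of the study".

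Protocol section 5 (Risks) states: "Subjects are free to withdraw from the study at any time". It also lets the investigator remove a participant for whom continuing is inadvisable. It does not mention data collection after either event.

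For change from baseline the SAP says: "we used paired t-tests for normally distributed variables and Wilcoxon signed-rank tests for non-normally distributed variables". Its feasibility measures include the "percentage of participants who withdrew or were lost to follow-up". It names no analysis set or missing-data rule, and does not commit to giving the number of pairs per outcome.

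**The concern.** The first goal of the study is "to examine the feasibility and acceptability of a pilot of ONBOARD for adults with T1D". People who leave after one or two sessions may be the best placed to say what was not acceptable, yet the text describes no step that asks them. If the follow-up sentence is applied as written, ONBOARD would be refined on the views of those who stayed.

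The second goal includes change in diabetes distress. A paired test needs a baseline and a follow-up value from the same person. Someone with no follow-up survey drops out of the test, and the effect size then describes finishers. The mean change would look too favourable if stoppers would have done worse, and too unfavourable if they would have done better. It would be about right if they would have changed by the same amount.

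**Working it through.** There is no figure in the plan to reproduce: the documents give no expected dropout, SD, effect size or precision target. The check has two parts.

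**1. Which data depend on finishing the sessions, on a literal reading**

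- Follow-up survey, including distress: yes (Protocol 2.a).
- Focus group, the stated source of qualitative data: yes (Protocol 2.a and 2.g).
- Follow-up device download, and hence time in range: no such condition (Protocol 2.a, separate paragraph).
- Withdrawal and loss percentages: no. They count stoppers who withdraw or are lost, but do not record their views or show how many pairs lie behind each test.

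**2. What early stopping could do to a survey change score (illustration)**

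From the documents: N = 20 to 40 (SAP). Assumed: the share stopping early, d = 10%, 20% or 30%; and the gap, meaning finishers' mean change minus stoppers' mean change in SD of change, with positive values where finishers do better.

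- Pairs: n = N × (1 − d).
- Shift = finisher mean − [(1 − d) × finisher mean + d × stopper mean] = d × gap.
- 95% half-width of the mean paired change, in SD of change = t(0.975, n − 1)/√n. For n = 18: 2.110/4.243 = 0.497.

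| N | d | Without follow-up | Pairs n | Half-width | Shift, gap 0.5 | Shift, gap 1.0 |
|---|---|---|---|---|---|---|
| 20 | 10% | 2 | 18 | 0.497 | 0.05 | 0.10 |
| 20 | 20% | 4 | 16 | 0.533 | 0.10 | 0.20 |
| 20 | 30% | 6 | 14 | 0.577 | 0.15 | 0.30 |
| 40 | 10% | 4 | 36 | 0.338 | 0.05 | 0.10 |
| 40 | 20% | 8 | 32 | 0.361 | 0.10 | 0.20 |
| 40 | 30% | 12 | 28 | 0.388 | 0.15 | 0.30 |

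With a gap of 0 the shift is 0. With a negative gap the sign reverses. The non-zero shifts run from 0.05/0.497 = 10% to 0.30/0.388 = 77% of the half-width, and none exceeds it.

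**The case against.** The strongest reply is that the opening phrase of the follow-up sentence only says when the assessment happens. The payment section supports this: the survey and focus group are paid separately from the sessions and tied to the end of the study, so partial completion seems to be foreseen. This stands. A reader might infer that early stoppers are barred from follow-up, but the documents do not say so. They also do not say that stoppers are invited, and one sentence would settle it.

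A second reply is that this is a small pilot described as descriptive, and that the focus group asks about individual sessions, so holding it after delivery is reasonable. That also stands, and people who attended few sessions can answer only part of it. But feedback on acceptability from finishers alone leaves a gap in what the pilot is meant to learn, and descriptive results still need denominators.

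A third reply is that attrition is already reported. It is, as an overall percentage. That does not give the reasons for stopping or the number of pairs per outcome.

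Finally, Protocol section 1 and the SAP are written in the past tense, so data collection may be over. If so, the change to follow-up no longer applies and only the reporting remains.

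**Conclusion.** The point holds as a gap in the described follow-up that is cheap to close. On the literal text, survey change and refinement feedback come only from finishers. The clearest loss is the feedback: 2 to 12 people unheard, for N = 20 to 40 and an assumed 10% to 30% stopping early.

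Three stronger readings are not supported.

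- *The improvement in distress is inflated.* The documents give neither a session-dropout rate nor any information on how stoppers fare, so neither direction nor size can be derived. The 27% in Protocol section 3.a refers to quitting CGM within the first year and cannot stand in for session dropout. The tabulated shifts rest wholly on assumed inputs.
- *Time in range is also limited to finishers.* The follow-up download carries no four-session condition.
- *Participants without baseline CGM data will be left out unreported.* Eligibility admits people not using CGM regularly, so some may lack a baseline time in range. That is a separate matter from stopping early. The SAP does not promise this count, but nothing says it will be withheld.

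**What to change.** **Protocol section 2.a, if follow-up is still ahead.** State that the follow-up survey and feedback are offered to every enrolled participant, whatever number of sessions was attended. Feedback can be the focus group or the same questions placed in the survey. The time point is when session 4 took place or would have been due; with sessions three weeks apart, that is 3 × 3 = 9 weeks after session 1. Except those who decline further contact, and those whom the investigator removed because continuing was inadvisable.

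**SAP.** Give the number of pairs for each outcome and, for time in range, the number of participants without baseline CGM data.

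**If data collection is over.** Report these numbers and state that survey change and feedback describe only those with follow-up data.

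**Cost.** One sentence in the protocol, a few lines in the SAP and a few more reminders; the survey is already online and the sessions are held by video. Some answers from people who attended few sessions will be partial, and not everyone invited will respond. The estimated change may turn out less favourable.

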4. PARTICIPANT POPULATION

- a. Planned Enrollment

We plan to enroll up to 40 participants.
- b. Age, Gender, and Ethnic Background
- c. We will actively recruit equal numbers of males and females between 18 and 50 years of age. Females are expected to comprise approximately 50% of the adult study sample. The study will not select with respect to the racial or ethnic background of the subjects as there are no race- or ethnic-specific hypotheses. The final study sample will be representative of the diverse ethnic population of patients in the Stanford Hospital & Clinics outpatient diabetes program and in the ethnically diverse Bay Area, with approximately 50% Caucasian participants, 25% Hispanic, 20% Asian, 2% African American, 3% Other. Vulnerable Populations
- d. Rationale for Exclusion of Certain Populations

NA
- e. Stanford Populations

NA
- f. Healthy Volunteers

NA
- g. Recruitment Details

Recruitment procedures will include direct contact and advertisements/flyers in clinics and postings with online Bay Area groups (e.g., JDRF, ADA, Carb DM), as well as referrals from treating physicians. Treating physicians may provide a study brochure which patients may use to contact study staff directly. Alternately, treating physicians may request permission for study staff to speak with the potential participant about the study during an appointment for usual care or to follow up with a phone call or email. We will also recruit from an independent list of non-Stanford clinic adults in the larger San Francisco Bay Area who have participated in closed loop trials at Stanford who have provided consent for contact about future trials (IRB-approved database).
- h. Eligibility Criteria
 - i. Inclusion Criteria
 1. Subject is age 18-50 years at time of screening
 2. Subject is within first year of continuous glucose monitor use OR has not been using CGM regularly in the past 6 months
 3. Subject has a clinical diagnosis of type 1 diabetes
 4. Subject comprehends spoken and written English
 - Exclusion Criteria

1. Subject has a medical disorder that in the judgment of the investigator will interfere with completion of any aspect of the protocol.
2. Subject has a neurologic disorder that in the judgment of the investigator will affect completion of the protocol.

i. Screening Procedures

Screening procedures include a review of inclusion/exclusion criteria to assess eligibility. This information will be verbally elicited from potential participants.

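### Does the follow-up A1c need a draw date after session 4 before it can be compared with baseline?

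*Protocol*

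**What the plan says.** Protocol Section 2.a asks, where one exists, for "a hemoglobin A1c result obtained in the 3 months prior to study enrollment". Participants then "complete ONBOARD sessions, each 3 weeks apart". The follow-up survey comes after the fourth session. The sentence on the second A1c stands after the survey and reads: "If a hemoglobin A1c result was obtained during the course of the study, we will ask participants to provide this", with the medical record as the alternative source. Section 4.m states that "participation in the study will require approximately 3 months".

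On use of the data, Section 2.g calls the quantitative analyses descriptive and says they will "examine differences between baseline and post-intervention in terms of psychosocial variables, technology attitudes, and health outcomes". The SAP gives its paired tests this aim: "To examine changes from baseline to post-intervention in primary and secondary outcome variables". It does not list those variables. Protocol Section 1 names time in range and diabetes distress as the outcomes for preliminary evidence. A1c appears in neither place as something to be analysed.

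Eligibility (Section 4.h) includes a person who "has not been using CGM regularly in the past 6 months". For non-users who want CGM, Section 2.a adds that "we will work with the clinical team to get them started via standard clinical procedures".

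**The concern.** The baseline A1c has a window and the survey is tied to the end of the sessions, but the second A1c is tied only to the study period. A result drawn after enrolment and before session 4, or even before session 1, would qualify. If it were entered as the follow-up value, the change reported as baseline to post-intervention would include people who had not finished the intervention.

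A1c averages glucose over preceding weeks, so an early draw also reflects time before ONBOARD and would understate the part of the change due to it. A CGM start between the two results pushes the other way, so the direction of the net bias is not fixed. With several results and no selection rule, the choice among them would also be open. At stake would be one before-after estimate in a single-arm pilot of 20 to 40 people.

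**Working it through.** **Schedule.** Inputs: four sessions at 3-week intervals (Protocol 2.a) and about 3 months of participation (4.m).

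- Session 1 to session 4: (4 − 1) × 3 = 9 weeks.
- 3 months: 365.25/12 × 3/7 = 13.04 weeks, leaving about 4 weeks for everything else. The schedule fits the stated 3 months.
- Share of the window before session 4, with session 1 at enrolment: 9/13.04 = 69%. With session 1 four weeks after enrolment: 13/13.04 = 99.7%.
- Interval between the two A1c results: from near 0 to about 2 × 13.04 = 26 weeks.

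**How much of an effect an A1c would capture.** The documents give no draw dates and no averaging period, so the following are assumptions: sessions at weeks 0, 3, 6 and 9; draw dates spread evenly over weeks 0-13; A1c an equal-weight mean over the previous L weeks, with L = 12 or 8.

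- Immediate full effect at week 0: a draw at week t captures min(t/L, 1).
 - Weeks 0-9: L = 12 gives (81/24)/9 = 0.375; L = 8 gives (4 + 1)/9 = 0.556.
 - Weeks 9-13: L = 12 gives (2.625 + 1)/4 = 0.906; L = 8 gives 1.000.
- Effect building linearly over weeks 0-9, then flat: averaging that curve over the previous L weeks gives the second row.
- No ONBOARD effect, CGM started 4 weeks before session 1 and after the baseline A1c: a draw captures min((t + 4)/L, 1) of the CGM-start effect.

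| Scenario | Draws in weeks 0-9 | Draws in weeks 9-13 |
|---|---|---|
| Immediate ONBOARD effect | 38-56% | 91-100% |
| Gradual ONBOARD effect | 13-19% | 54-74% |
| CGM start only | 70-89% | 100% |

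The last row shows direction only. If that CGM start is the study-supported one, draws running to week 13 imply at least 4 + 13 = 17 weeks of participation, more than the stated 3 months.

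**What a cutoff after session 4 would do.** It keeps the right-hand column. Capture of an ONBOARD effect improves, but under gradual build-up it remains partial on average across the whole remaining window. The share of a CGM-start effect rises.

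The price is the share of results dated before session 4. With session 1 at enrolment this is 69% for evenly spread dates, (9/13)² = 48% if dates cluster late, and 1 − (4/13)² = 91% if they cluster early. A gap between enrolment and session 1 raises the evenly spread figure towards 100%. Not everyone will have a second A1c at all, so the number of usable pairs cannot be projected from the documents.

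**The case for a change.** The best case for a change is that it is cheap. Two or three sentences in the SAP and a recorded draw date would settle A1c's role and keep the post-intervention label accurate. The position of the A1c sentence after the survey does not rescue the wording: it shows when results are gathered, not when blood was drawn. The protocol collects A1c before and during the study, and its background section treats A1c as closely linked to later complications. Analysing it among the health outcomes of Section 2.g is therefore the natural reading. Calling the analyses descriptive does not remove the issue either, since the SAP applies paired tests and effect sizes.

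The reading of the text and the schedule arithmetic stand: a mid-intervention result does qualify. Two parts do not carry over into a required change. First, the harm needs an analysis that neither document states, of a value obtained only by chance. The background section itself argues for time in range as the more sensitive and specific measure. Second, the CGM-start argument does not support a date cutoff. That confounding affects any before-after comparison here, and later draws carry more of it.

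**Conclusion.** The gap in wording is real but no change follows. The study's stated aims are feasibility, acceptability, and preliminary evidence on time in range and diabetes distress. None of these depends on when an opportunistic A1c was drawn, so a fixed window would leave the conclusions as they are. If A1c is reported, a competent analyst would look at the draw dates, describe as post-intervention only what was drawn after session 4, and present the rest as supportive.

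Making that a binding rule is a matter on which reasonable statisticians would differ. Under evenly spread dates it removes 69% or more of the results. In return, capture rises from 38-56% to 91-100% for an immediate effect, but only from 13-19% to 54-74% for a gradual one. These shares rest on assumed averaging periods of 8-12 weeks, assumed draw dates and assumed effect shapes. Only the 9-week span and the 13-week window come from the documents.
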